### **3.1.4. Dose-Limiting Toxicity (DLT) Analysis Set**

The DLT Analysis Set includes all subjects in the Safety Analysis Set who complete all treatment and safety procedures through Day 28, inclusive, or experienced a DLT prior to Day 28, exclusive. During the DLT assessment window, if a subject who fails to receive study drug for at least 21 days for reasons other than DLT, another subject will be enrolled at the same dose level for replacement. For subjects who are replaced but received at least 1 dose of study drug, they will be included in the Safety Analysis Set and not in the DLT Analysis Set.

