The SRT will consist of at least one investigator and the following Gilead Sciences, Inc. (Gilead) study team members: the Gilead medical monitor, representatives from Drug Safety and Public Health (DSPH) and Biostatistics. Others may be invited to participate as members of the SRT if additional expertise is desired. The Gilead medical monitor serves as the chair of the SRT. Investigators whom have enrolled a subject into the cohort the SRT is evaluating is/are required to participate in the dose escalation/expansion decision.

The recommended dose of GS-5829 to be combined with fulvestrant in the Randomized Phase 2 Dose Expansion part of this study will be determined based on the data available in the Phase 1b Dose Escalation portion of this study and from studies GS-US-350-1599 and GS-US-350-1604. The recommended dose will not exceed the MTD identified by the Phase 1b dose escalation

from this study. At least 6 subjects should have already been treated and evaluated at that dose level prior to enrolling subjects in the Randomized Phase 2 Dose Expansion.

Dose Limiting Toxicity (DLT) Definition

A DLT is a toxicity defined below and considered possibly related to GS-5829 if occurring during the DLT assessment window (Day 1 through Day 28) in each combination therapy cohort:

[figure not shown]
- Grade ≥ 4 neutropenia (absolute neutrophil count [ANC] $< 500/\text{mm}^3$)
- Grade ≥ 3 neutropenia (ANC $< 1000/\text{mm}^3$) with fever (a single temperature of $> 38.3^\circ\text{C}$ or a sustained temperature of $\geq 38^\circ\text{C}$ for more than one hour)
- Grade ≥ 3 thrombocytopenia
- Grade ≥ 2 bleeding (e.g. gastrointestinal, respiratory, epistaxis, purpura)
- Grade ≥ 3 or higher non-hematologic toxicity, except:
 - Grade 3 nausea or emesis with maximum duration of 48 hours on adequate medical therapy
 - Grade 3 diarrhea which persists for < 72 hours in the absence of adequate medical therapy
- Grade ≥ 2 non-hematologic treatment-emergent adverse event (TEAE) that in the opinion of the investigator is of potential clinical significance such that further dose escalation would expose subjects to unacceptable risk
- Treatment interruption of ≥ 7 days due to unresolved toxicity

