6.12. Replacement of Subjects

If a subject in the Phase 1b portion of the study is withdrawn from the study for any reason other than a DLT prior to completion of the DLT assessment window, a replacement subject will be enrolled at the same dose level as the replaced subject. To be evaluable for the DLT observation, a subject must receive at least 21 doses of GS-5829, complete all safety procedures through Day 28, or experience a DLT prior to Day 28.

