8.1.2. Primary Endpoints

Phase 1b Dose Escalation:

- Safety profile and tolerability of the combination of GS-5829 and fulvestrant as assessed by DLTs through Day 28 at each dose level of GS-5829

Randomized Phase 2 Dose Expansion:

- PFS defined as the interval from date of randomization to the earlier of the first documented confirmed disease progression or death from any cause

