8.2.1.4. DLT-Evaluable Analysis Set

The DLT-Evaluable Analysis Set includes all Phase 1b Dose Escalation subjects in the Safety Analysis Set who complete all treatment and safety procedures through Day 28, or experienced a DLT prior to Day 28. Subjects who are not evaluable for DLT determination may be replaced.

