##### **3.1.2. Full Analysis Set**

The Full Analysis Set (FAS) includes all subjects who were enrolled and received at least 1 dose of any study drug (GS-5829, fulvestrant or exemestane). This is the primary analysis set for the analyses of efficacy. Throughout this SAP, study drug is defined as any drug in the combination therapy (GS-5829, fulvestrant or exemestane) unless specified otherwise.

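### SAP 3.1.4 leaves a Day 28 DLT out of its DLT criterion although the endpoint runs through Day 28, its treatment requirement differs from Protocol 6.12, and no DLT n/N by dose is planned

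*SAP*

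**What the plan says.** **Window and endpoint.** Protocol 3.2 counts a listed toxicity as a DLT "if occurring during the DLT assessment window (Day 1 through Day 28", so Day 28 is included. Protocol 8.1.2 makes the Phase 1b primary endpoint the safety and tolerability of GS-5829 with fulvestrant "as assessed by DLTs through Day 28 at each dose level of GS-5829".

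**Evaluability** is defined in three places:

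- Protocol 6.12: "a subject must receive at least 21 doses of GS-5829, complete all safety procedures through Day 28", "or experience a DLT prior to Day 28".
- Protocol 8.2.1.4: subjects "who complete all treatment and safety procedures through Day 28, or experienced a DLT prior to Day 28".
- SAP 3.1.4: subjects who "complete all treatment and safety procedures through Day 28, inclusive, or experienced a DLT prior to Day 28, exclusive". The next sentence provides for a replacement "if a subject who fails to receive study drug for at least 21 days for reasons other than DLT". Replaced subjects who took a dose stay in the Safety Analysis Set but not in the DLT Analysis Set.

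**Output.** SAP 7.1.7.1 plans a by-subject listing of DLT events, as Protocol 8.6.4 does. SAP 3.1 and 4.1 report the size of the DLT Analysis Set by dose cohort. The protocol synopsis (Statistical Methods, Phase 1b) says that the incidence of DLTs will be evaluated.

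**The concern.** An event that counts toward the primary endpoint should by itself place its subject in the set used to measure that endpoint. For a DLT on Day 28 it does not. The protocol's phrase could pass as loose drafting, but the SAP adds the word exclusive and so fixes the cutoff a day short of the window.

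The treatment requirement also differs between the three definitions, so the denominator depends on which one the programmer follows. And no table joins a numerator to that denominator, although the endpoint is stated by dose level.

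The study ended in Phase 1b (SAP 1), so this endpoint is its main result. Cohorts are of 3 (Protocol 3.2), so one subject visibly changes the reported proportion.

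**Working it through.** The plan states no DLT figure to reproduce. The first check is to take each kind of subject through the three definitions as literally worded. I read Protocol 6.12 as (21 doses and safety procedures) or DLT; its punctuation does not make this certain.

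| Subject | Protocol 6.12 | Protocol 8.2.1.4 | SAP 3.1.4 |
|---|---|---|---|
| DLT on Days 1–27 | in | in | in |
| DLT on Day 28, all treatment and procedures complete | in | in | in (completion criterion) |
| DLT on Day 28, 21–27 doses, procedures complete | in (21 doses) | out | out |
| DLT on Day 28, a safety procedure missed or fewer than 21 doses | out | out | out |
| No DLT, 28 doses, procedures complete | in | in | in |
| No DLT, 21–27 doses, procedures complete | in | out | out by the first sentence, yet not replaced by the second |
| No DLT, fewer than 21 doses | out | out | out, replaced |

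Rows 3 and 4 are the Day 28 gap. Both subjects have a DLT inside the Protocol 3.2 window. Row 3 includes a subject whose Day 28 dose is held because of that day's DLT, so the toxicity itself makes treatment incomplete.

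Row 6 is the treatment gap. With 28 daily doses, missing k days leaves 28 − k: 1 to 6 missed days leave 27 to 22 doses, and 7 leave 21 (21/28 = 75%). The interruption criterion in Protocol 3.2 applies only to toxicity interruptions of 7 days or more, so a shorter gap is not by itself a DLT.

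**Size.** The documents give no Phase 1b DLT counts, so these cohorts are hypothetical. Inputs are 3 subjects per cohort and the minimum of 6 at a dose taken into Phase 2 (both Protocol 3.2). The exact 95% interval runs from the 0.025 quantile of Beta(x, n − x + 1) to the 0.975 quantile of Beta(x + 1, n − x). With x = 0 the lower limit is 0 and the upper limit is 1 − 0.025^(1/n), for example 1 − 0.025^(1/5) = 52.2%.

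| Subject left out | All counted | After exclusion |
|---|---|---|
| Day 28 DLT, cohort of 3 | 1/3 = 33.3% (0.8–90.6) | 0/2 = 0% (0–84.2) |
| Day 28 DLT, 6 subjects | 1/6 = 16.7% (0.4–64.1) | 0/5 = 0% (0–52.2) |
| No DLT, 21–27 doses, 6 subjects | 1/6 = 16.7% (0.4–64.1) | 1/5 = 20.0% (0.5–71.6) |
| No DLT, 21–27 doses, 6 subjects | 0/6 = 0% (0–45.9) | 0/5 = 0% (0–52.2) |

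**Output.** SAP 3.1 and 4.1 give N by dose cohort. No table gives the number with a DLT, and no analysis is assigned to the DLT Analysis Set. Listings are on the All Enrolled Analysis Set (SAP 3).

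**The case against.** **The Day 28 case is nearly empty.** A subject who completed everything enters anyway. A toxicity hold over Days 22–28 reaches seven days on Day 28, but it follows an event that began earlier, and the SAP classifies adverse events by onset (7.1.5). Dated by onset, that DLT falls before Day 28. This stands as a limit on frequency. It leaves a DLT with onset on Day 28 plus a missed dose or procedure, and for that subject the rule is wrong.

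**SAP 3.1.4 should be read whole.** A subject with 21 to 27 doses is not replaced, which suggests agreement with Protocol 6.12. That may well be the intent. But the sentence defining membership still asks for all treatment, and nothing says that held or missed days count as complete.

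**The table is a preference.** Protocol 8.6.4 asks only for a listing, N is already planned, and n can be counted by hand. All true; yet the synopsis promises incidence and the endpoint is by dose level.

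Three stronger readings are not supported:

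- *A reader might infer that Day 28 shifts when exemestane or fulvestrant starts before C1D1*, because SAP 3.8.1 counts study day from the first dose of study drug. SAP 3.1.4 says Day 28, in the context of the DLT window; where the SAP means the other count it writes Study Day 1 (3.8.3, 6.1.1). Protocol 3.2 counts cohort follow-up from C1D1 of GS-5829.
- *A reader might infer that the background drug can satisfy the 21-day replacement rule*, because in the SAP "study drug is defined as any drug in the combination therapy". The Protocol 8.1.2 endpoint names only the fulvestrant combination. Scheduled fulvestrant falls on at most two days of the window (Days 1 and 15), so 21 days still need GS-5829 on at least 21 − 2 = 19.
- *A reader might infer that the SAP should declare the MTD or RP2D undetermined and the final dose–DLT model not run.* The model is rebuilt after each cohort and the Safety Review Team decides the RP2D (Protocol 3.2). Nothing in the documents says that the model was not run.

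**Conclusion.** Wrong as written, and minor. The DLT criterion of SAP 3.1.4 ends a day before the window and endpoint it serves; Protocol 6.12 and 8.2.1.4 have the same fault in looser words. The 21-dose and all-treatment requirements are not reconciled. The DLT Analysis Set feeds no planned result.

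The practical effect is confined to the final report. Enrolment ended in Phase 1b and all subjects have stopped study drug (SAP 1), so a correction now changes no escalation or replacement decision, and the documents give no sign that a past decision was affected. Whether any subject falls in the gaps is unknown. The 1/6 against 0/5 or 1/5 comparisons show only what one subject can do in a group of that size, and the intervals overlap heavily. The conclusion rests on the literal wording and on the natural reading of Protocol 6.12.

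**What to change.** 1. In SAP 3.1.4, include every subject with a DLT from Day 1 through Day 28 inclusive of the DLT window, whether or not treatment and procedures were completed.
2. Reconcile Protocol 6.12, Protocol 8.2.1.4 and SAP 3.1.4 into one evaluability definition for the analysis set, stated in GS-5829 exposure, saying whether held or missed days count as completed treatment. The threshold is for the sponsor to choose. Settle it before data finalization.
3. Add one table on the DLT Analysis Set: subjects with a DLT over DLT-evaluable subjects, by dose cohort within treatment group, with exact 95% intervals.

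The cost is a few sentences of SAP text and one small table. No new data and no model run are needed.

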### **3.1.5. Pharmacokinetic Analysis Set**

The Pharmacokinetic (PK) Analysis Set will include all enrolled subjects who received at least 1 dose of study drug and have at least 1 nonmissing postdose concentration value reported by the PK laboratory. Subjects who received concomitant medications prohibited in this study will be excluded from the PK analysis set. This is the primary analysis set for all PK analyses.

## **3.2. Subject Grouping**

Subjects will be categorized by treatment group (A [GS-5829 + exemestane] or B [GS-5829 + fulvestrant]) and dose cohort. Summaries will be presented by dose cohort within each treatment group and overall, unless specified otherwise.

Subjects will be grouped according to the actual treatment they received.

## **3.3. Strata and Covariates**

No stratum and covariates will be included in efficacy and safety analyses.

## **3.4. Examination of Subject Subgroups**

There are no prespecified subject subgroupings for efficacy and safety analyses.

## **3.5. Multiple Comparisons**

Adjustments for multiplicity will not be made, because no formal statistical testing will be performed in this study.

## **3.6. Missing Data and Outliers**

### **3.6.1. Missing Data**

In general, missing data will not be imputed unless methods for handling missing data are specified. Exceptions are presented in this document.

For missing last dosing date of study drug, imputation rules are described in Section 4.2.1. The handling of missing or incomplete dates for the completion of prior anticancer therapy is described in Section 5.4, for death and the initiation of new anticancer therapy in Section 6.1.1, for AE onset in Section 7.1.5.2, and for prior and concomitant medications in Section 7.4.

### 3.6.2. Outliers

Outliers will be identified during the data management and data analysis process, but no sensitivity analyses will be conducted. All data will be included in the data analysis.

### 3.7. Data Handling Conventions and Transformations

Age (in years) on the first dosing date of study drug will be used for analyses and presentation in listings. If an enrolled subject was not dosed with any study drug, the enrollment date will be used instead of the first dosing date of study drug. If only the birth year is collected on the CRF, “01 July” will be used for the unknown birth day and month for the purpose of age calculation. If only birth year and month are collected, “01” will be used for the unknown birth day.

Non-PK data that are continuous in nature but are less than the lower limit of quantitation (LOQ) or above the upper LOQ will be imputed as follows:

- A value that is 1 unit less than the LOQ will be used to calculate descriptive statistics if the datum is reported in the form of “ $< x$ ” (where x is considered the LOQ). For example, if the values are reported as  $< 50$  and  $< 5.0$ , values of 49 and 4.9, respectively, will be used to calculate summary statistics. An exception to this rule is any value reported as  $< 1$  or  $< 0.1$ , etc. For values reported as  $< 1$  or  $< 0.1$ , a value of 0.9 or 0.09, respectively, will be used to calculate summary statistics.
- A value that is 1 unit above the LOQ will be used to calculate descriptive statistics if the datum is reported in the form of “ $> x$ ” (where x is considered the LOQ). Values with decimal points will follow the same logic as above.
- The LOQ will be used to calculate descriptive statistics if the datum is reported in the form of “ $\leq x$ ” or “ $\geq x$ ” (where x is considered the LOQ).

If methods based on the assumption that the data are normally distributed are not adequate, analyses may be performed on transformed data or nonparametric analysis methods may be used, as appropriate.

Natural logarithm transformation will be used for plasma/blood concentrations and analysis of PK parameters. Plasma concentration values that are below the limit of quantitation (BLQ) will be presented as “BLQ” in the concentration data listing. Values that are BLQ will be treated as 0 at predose time points, and one-half the value of the LOQ at postbaseline time points.

The following conventions will be used for the presentation of summary and order statistics:

- If at least 1 subject has a concentration value of BLQ for the time point, the minimum value will be displayed as “BLQ.”
- If more than 25% of the subjects have a concentration data value of BLQ for a given time point, the minimum and Q1 values will be displayed as “BLQ.”

- If more than 50% of the subjects have a concentration data value of BLQ for a given time point, the minimum, Q1, and median values will be displayed as “BLQ.”
- If more than 75% of the subjects have a concentration data value of BLQ for a given time point, the minimum, Q1, median, and Q3 values will be displayed as “BLQ.”
- If all subjects have concentration data values of BLQ for a given time point, all order statistics (minimum, Q1, median, Q3, and maximum) will be displayed as “BLQ.”

PK parameters that are BLQ will be imputed as one-half LOQ before log transformation or statistical model fitting.

### **3.8. Analysis Visit Windows**

#### **3.8.1. Definition of Study Day**

Study day will be calculated from the first dosing date of study drug and derived as follows:

- For postdose study days: Assessment Date – First Dosing Date + 1
- For days prior to the first dose: Assessment Date – First Dosing Date

Therefore, study day 1 is the day of the first dose of study drug administration.

#### **3.8.2. Analysis Visit Windows**

The nominal visit as recorded on the CRF will be used when data are summarized by visit. Any data relating to unscheduled visits will not be assigned to a particular visit or time point.

However, the following exceptions will be made:

- An unscheduled visit prior to the first dosing of study drug may be included in the calculation of the baseline value, if applicable.
- Unscheduled visits after the first dose of study drug will be included in determining the maximum postbaseline toxicity grade.
- For subjects who prematurely discontinue from the study, early termination (ET) data will be assigned to what would have been the next scheduled visit where the respective data were scheduled to be collected.
- Data collected on a follow-up visit will be summarized as a separate visit, and labeled “Follow-up Visit.”
- Data obtained after the follow-up visit or last dose date plus 30 days (whichever is later) will be excluded from the summaries, but will be included in the listings.

### **3.8.3. Selection of Data in the Event of Multiple Records in an Analysis Visit Window**

Depending on the statistical analysis method, single values may be required for each visit. For example, change from baseline by visit usually requires a single value, whereas a time-to-event analysis would not require 1 value per visit.

If multiple valid, nonmissing, continuous measurements exist in an visit, records will be chosen based on the following rules if a single value is needed:

- In general, the baseline value will be the last nonmissing value on or prior to Study Day 1, unless specified differently. If multiple measurements occur on the same day, the last nonmissing value prior to the first dosing date of study drug will be considered as the baseline value. If these multiple measurements occur at the same time or the time is not available, the average of these measurements (for continuous data) will be considered the baseline value.
- For postbaseline values:
  - The record closest to the nominal day for that visit will be selected.
  - If there are 2 records that are equidistant from the nominal day, the later record will be selected.
  - If there is more than 1 record on the selected day, the average will be taken, unless otherwise specified.

For central ECG data, there may be triplicates at the same nominal day/timepoint for each subject. The average of the triplicates should be used as baseline or postbaseline values at each visit and for selecting the maximum postbaseline values.

If multiple valid, nonmissing, categorical measurements exist in an analysis window, records will be chosen based on the following rules if a single value is needed:

- For baseline, the last available record on or prior to the date of the first dose of study drug will be selected. If there are multiple records with the same time or no time recorded on the same day, the value with the lowest severity will be selected (eg, normal will be selected over abnormal for safety electrocardiogram (ECG) findings).
- For postbaseline visits, if there are multiple records with the same time or no time recorded on the same day, the value with the worst severity within the window will be selected (eg, abnormal will be selected over normal for safety ECG findings).

## 4. SUBJECT DISPOSITION

### 4.1. Subject Enrollment and Disposition

The summary of subject disposition will present the number of subjects screened, subjects enrolled and subjects in the following categories by dose cohort within each treatment group, and overall:

- Safety Analysis Set
- Full Analysis Set
- DLT Analysis Set
- Discontinued study drug with reasons for discontinuation of study drug
- Completed study
- Discontinued the study with reasons for discontinuation of study

For the status of study drug and study completion and reasons for discontinuation, the number and percentage of the subjects in each category will be provided. The denominator for the percentage calculation will be the total number of subjects in the safety analysis set corresponding to that column.

The following by-subject listing will be provided by subject identification (ID) number in ascending order to support the above summary tables:

- Reasons for premature study drug and study discontinuation.

### 4.2. Extent of Study Drug Exposure and Adherence

Extent of exposure to GS-5829 will be examined by assessing the total duration of exposure to GS-5829 and the level of adherence to GS-5829 specified in the protocol.

#### 4.2.1. Duration of Exposure to GS-5829

Total duration of exposure to GS-5829 will be defined as last dosing date of GS-5829 minus first dosing date of GS-5829 plus 1, regardless of any temporary interruptions in GS-5829 administration, and will be expressed in weeks using up to 1 decimal place (eg, 4.5 weeks).

If the last dosing date of GS-5829 is missing, the latest date among GS-5829 end date, clinical visit date, laboratory sample collection date, and vital signs assessment date that occurred during the on-treatment period will be used.

Partial dose start or stop dates for each dosing period will be imputed using the following algorithm:

- For dose stop date: If the day and month are missing but the year is available, then the imputed day and month will be the earliest from the following dates: 31 DEC, death date, end of treatment (EOT) date, EOS date, and (start date of the next dosing period – 1); If the day is missing but the month and year are available, , then the imputed day will be the earliest from the following dates: last day of the month, death date, EOT date, EOS date, and (start date of the next dosing period – 1).
- For dose start date: If the day and month are missing but the year is available, then the imputed day and month will be the earliest from the following dates: later of (01 JAN, and [stop date of the previous dosing period + 1]), and stop date of the associated dosing period; If the day is missing but the month and year are available, then the imputed day will be the earliest from the following dates: later of (first day of the month, and [stop date of the previous dosing period + 1]), and stop date of the associated dosing period.

The total duration of exposure to GS-5829 will be summarized using descriptive statistics and using number and percentage of subjects exposed through the following time periods: 1 day, 4 weeks, 8 weeks, 16 weeks, 24 weeks, 36 weeks and 48 weeks. Summaries will be provided by dose cohort within each treatment group for the Safety Analysis Set.

